1.2 Schedule of Activities

Study Procedure	Screening	Baseline (Treatment)	Post Baseline Visit Schedule							
	Day (-28) through Day (-1)	Day 1	Day 2	Day 4	Day 7	Day 14	Day 21	Day 28	Day 56	Day 84
Signed informed consent	X									
Medical history	X									
Physical Exam	X				X					X
Concomitant Medication	X	X	X	X	X	X	X	X	X	X
Pregnancy β -hCG	X									
Pregnancy urine test (women)		X								X
Weight measurements	X	X						X		X
Height measurement	X									
Biochemistry Lab parameters	X		X		X			X		X
ECG	X				X					X
Vital signs	X	Pre X post	X	X	X	X	X	X	X	X
Randomization	X									
Injection of RZL-012		X								
Clinician Chin Assessment Tool (C-CAT)	X	X						X	X	X
Subject- Self-Chin Assessment Tool (S-CAT)	X	X						X	X	X
Subject's Satisfaction questionnaire for SMF appearance	X							X	X	X
2D Standardized photography	X		X	X	X	X	X	X	X	X
MRI	X									X
AEs including VAS		X	X	X	X	X	X	X	X	X

2.0 INTRODUCTION

1.1. Study Rationale

The recent clinical study (RZL-012-SMF-P2b-US-001) was a double-blind, randomized, three-arm, placebo-controlled Phase 2b study that tested the efficacy and safety of RZL-012 injections into the submental fat in 151 subjects. Single administration of high dose RZL-012 (50mg/ml) resulted in a clinically meaningful reduction in submental fat. The efficacy of the RZL-012 high dose was higher than that of the low dose and of the placebo. Local injection-site reactions were the most commonly reported AEs with injection-site pain, nodules induration and edema being clearly RZL-012 related. Injection-site severe swelling in the submental area was shown to be associated with additional AEs such as dysphagia, dysphonia, and dyspnea.

This clinical trial will assess ways to reduce AEs related to swelling and pain.

1.2. Scientific Background

RZL-012 is a cytolytic drug - it disrupts cell membrane integrity which results in necrotic cell death. RZL-012 demonstrated a cell killing effect on cultured adipocyte, fibroblasts and HepG2 cells with IC₅₀ values ranging between 20-100 µM. In vivo pig studies demonstrated liponecrosis at the injection site, followed by a transient inflammatory response and finally, a healing process in which fibrotic tissue replaces previous fat tissue. Necrosis of fat tissue at the injection site was seen as early as 24 hours after injection and was still evident 2 weeks later but completely cleared by 12 weeks post dosing. A macrophage-mediated inflammatory response was also prominent at 24 hours and 14 days after injection with only minimal signs of inflammation remaining by 12 weeks post dosing. Fibrosis showed a different pattern compared with liponecrosis and inflammation, starting at 14 days post dosing and becoming much more prominent at 12 weeks post dosing. In essence, RZL-012 enabled de-novo generation of fibrotic tissue to replace excess fat tissue at selected anatomical sites.

To date, Raziel has conducted several clinical studies under INDs to evaluate the safety and efficacy of RZL-012 for local fat reductions, including obesity (INDs 119941, 133324), lipomas of Dercum's Disease patients and SMF (IND 135762) and SMF and flank reduction (IND 154260). Across all clinical trials approximately 222 subjects have received single doses of RZL-012 ranging from 5 mg to 412 mg per subject.

1.2.1. Non-Clinical Studies

The mechanism of action of RZL-012 has been studied in in-vitro studies and in in-vivo studies in pigs (domestic Yorkshire crossbred swine). Pigs were chosen for these studies because their subcutaneous fat resembles that of humans. RZL-012 injected into SC pig fat first caused liponecrosis at the injection site, followed by a transient inflammatory response and finally by a healing process in which fibrotic tissue replaced previous fat tissue.

Safety pharmacology studies of RZL-012 in male Sprague Dawley rats demonstrated that RZL-012 has no effects on the central nervous system functions, or on the respiratory system, on ECG parameters or blood pressure. Safety pharmacology studies of RZL-012 in domestic Yorkshire crossbred swine demonstrated no effects on ECG parameters or blood pressure.

Single and chronic toxicology studies were conducted in Sprague-Dawley rats and in pigs. Local, dose-related skin reactions included fibrosis, inflammation, degeneration/necrosis, atrophy and epidermal hyperplasia. Systemic reactions included increased blood urea nitrogen [BUN], increased creatinine and aspartate aminotransferase [AST] levels and histopathological changes in kidneys (necrosis in tubular epithelium).

Rat embryo-fetal development (EFD) and fertility and early embryo-fetal development (FEED; fertility) studies demonstrated no changes on fertility and reproduction in males and females.

Further details on mechanism of action, safety pharmacology, and toxicology of RZL-012 are provided in the investigator’s brochure (IB).

1.2.2. Clinical Studies

To date, approximately 222 subjects have received single doses of RZL-012 ranging from 5 mg to 412 mg per subject across 8 clinical trials (Table 1).

Table 1 Estimated Cumulative Exposure from Clinical Studies

Study Number	Study Population	RZL-012		Placebo
		N	Dose (mg)	N
RZL-012-P0-US-001	Healthy Subjects (Phase 0 obesity)	18	5-20	6
RZL-012-P2a-US-001	Healthy subjects (Phase 2a obesity)	24	40-180	7
RZL-012-FD-P2a-US-001	Lipedema (Phase 2a)	6	60-80	0
RZL-012-FD-P2a-US-001	DD (Phase 2a)	6	30-40	0
RZL-012-DD-P2b-US-001	DD (Phase2b)	29	40-240	18
RZL-012-SMF-P2a-US-001	Submental Fat (Phase 2a)	18	70-210	10
RZL-012-hADMEC14-001	Human ADME study	6	72.9	0
RZL-012-SMF-P2b-US-001	Submental Fat (Phase 2b)	103	142-270	48
RZL-012-FL-P2US-001	Subjects with Flank Fat	12	412	0
	Overall Total Number of Subjects	222	-	89

All clinical trials were conducted in the US, and in all trials RZL-012 was administered via multiple injections during a single injection session.

1.2.2.1. Clinical Trials in SMF

Three clinical trials have been conducted to assess the efficacy and safety of RZL-012 in reducing fat in the submental area. One trial (study RZL-012-SMF-P2a-US-001) was a single-blind, randomized, placebo-controlled, phase 2a, 2-cohort study. The second trial (study RZL-012-SMF-P2b-US-001) was a double-blind, randomized, three-arm, placebo-controlled Phase 2b study. Both studies were completed. The third trial (Study RZL-012-SMFC-P2-US-001) is An Open-Label Phase 2 Study to Compare the Pharmacokinetics, Efficacy and Safety of

RZL-012 in Chinese Subjects Seeking Submental Fat Reduction vs. Non-Chinese Subjects Seeking Submental Fat Reduction. Study enrollment has been initiated recently.

Study RZL-012-SMF-P2a-US-001

Study RZL-012-SMF-P2a-US-001.2 was a single-blind study conducted in 28 subjects with submental fat. An assessment of efficacy was based on the Physician global assessment scale, SMF volume change (MRI), and subject's Face-Q satisfaction questionnaire.

All subjects received a single dosing session and were followed up for 84 days. RZL-012 low dose (N=8) received an average injected dose of 80 mg/subject, RZL-012 high dose (N=10) an average injected dose of 158.5 mg/subject. Ten subjects received placebo. Based on a physician global assessment scale (physicians were not blinded to study treatment), 17/18 of RZL-012 treated subjects demonstrated an improvement in submental fat appearance on 84 days after treatment vs. baseline. None of the placebo subjects demonstrated any change in submental fat appearance on Day 84 vs. baseline. According to the Subject Face-Q Questionnaire (subjects were blinded to study treatment), subjects reported satisfaction regarding perceived effects of RZL-012 on submental fat appearance. The RZL-012 low dose group had a 2.4-fold increase in mean subject satisfaction score, the RZL-012 high dose group showed a 2.5-fold increase in mean subject satisfaction score while the placebo group did not demonstrate an improvement in satisfaction on Day 84 vs. baseline. These Clinician Reported Outcome (CRO) and Patient Reported Outcome (PRO) were correlated with the objective measure of MRI, determined on Day 84 vs. baseline. The high dose RZL-012 group showed a volume reduction of $-22.2\% \pm 14.9$ ($p < 0.05$ vs the placebo group), the low dose RZL-012 group showed a volume reduction of $-10.6\% \pm 14.5$ ($p = 0.67$ vs the placebo group, NS) and the placebo group demonstrated a volume reduction of $-0.4\% \pm 13.9$.

Study RZL-012-SMF-P2b-US-001

Study RZL-012-SMF-P2b-US-001 was a double-blind, randomized, three-arm, placebo-controlled Phase 2b study conducted in 151 subjects with submental fat. Forty-eight subjects were randomized to the placebo group, 53 subjects to the RZL-012 low dose (183.6 mg) group and 50 subjects to the RZL-012 high dose (270 mg) group. An assessment of efficacy was based on the Clinician Assessment Tool (C-CAT), Subject Self-Chin Assessment Tool (S-CAT); and SMF volume via MRI and caliper-measured submental thickness. Raziel met the primary and secondary endpoints of the study. The proportion of subjects that had an improvement of at least 1 grade using the C-CAT and proportion of subjects who had an improvement of at least 2 grades in both C-CAT and S-CAT in the same subject were statistically significantly higher in RZL-012 high dose vs. placebo. The MRI results demonstrated a volume reduction of -14.9%, -8.3% and no reduction in volume in RZL-012 high dose, low dose and placebo, respectively. Results were statistically significant.

The relationship between RZL-012 injection and a potential increase in liver enzymes is not completely understood. In preclinical studies which were conducted by Raziel, a rise in AST enzyme levels was observed in the high doses female rat group (20 mg/rat (about 80 mg/kg), equivalent to a human dose >900 mg/subject), returning to normal levels within 14 days of recovery. Raziel Therapeutics continues to monitor closely for any changes in liver enzymes.

1.3.2. Benefits

The cytolytic effect of RZL-012 has been demonstrated in non-clinical in-vitro and in-vivo studies. When administered into subcutaneous tissue, this cytolytic effect translates into a reduction in subcutaneous tissue. The reduction in submental fat has been demonstrated in Phase 2a and Phase 2b studies. Confirmatory Phase 3 studies will be conducted.

3.0 STUDY OBJECTIVES AND ENDPOINTS

3.1 Study Objectives

3.1.1 Primary Objective

- The primary objective of this study is to compare the benefits of lidocaine, methylprednisolone, Celecoxib + cetirizine or compression garments on RZL-012-induced adverse events.

3.1.2 Secondary Objectives

- To assess the safety profile of RZL-012 of combining lidocaine, methylprednisolone , Celecoxib + cetirizine or compression garment with RZL-012

3.2 Study Endpoints

3.2.1 Primary Endpoint

- Safety profile of combining lidocaine, methylprednisolone , Celecoxib +cetirizine or a compression garment with RZL-012.

3.2.2 Exploratory Endpoints

The secondary endpoints for the study are:

- Proportion of subjects who have at least a 1-grade improvement in the C-CAT on Day 84 versus baseline in subjects receiving RZL-012 alone or in combination with other medications.
- Proportion of subjects who have at least a 1-grade improvement in the S-CAT on Day 84 versus baseline in subjects receiving RZL-012 alone or in combination with other medications.
- Proportion of subjects who have at least a 1-grade improvement in both C-CAT and S-CAT on Day 84 versus baseline in subjects receiving RZL-012 alone or in combination with other medications.
- Proportion of subjects who have at least a 2-grade improvement in both C-CAT and S-CAT on Day 84 versus baseline in subjects receiving RZL-012 alone or in combination with other medications.
- Changes in SMF volume measured by MRI scans on Day 84 versus baseline in subjects

receiving RZL-012 alone or in combination with other medications.

- Satisfaction in subjects receiving RZL-012 alone or in combination with other medications.

4.0 STUDY DESIGN

4.1 Overall Design

This is a Phase 2, open-label, 2-stage, adaptive-design study in which subjects will be randomized into one of 5 treatment groups comprised of RZL-012 with or without additional study treatments:

1. RZL-012 alone
2. RZL-012 and 1% lidocaine with 1:100,000 epinephrine (on Day 1) – 5ml lidocaine will be injected 10 minutes before RZL-012 treatment.
3. RZL-012 and oral methylprednisolone dose pack (8 mg (2 tablets) on Day 1 before treatment followed by 16 mg after treatment (as per Instructions for Use)). From Day 2, a daily tapering off by 4 mg until Day 6 will be administered per Rx Instructions for use.
4. RZL-012 and Celecoxib and cetirizine (200 mg Celecoxib BID and 10 mg cetirizine BID on Days 1, 2, 3, 4, 5 and 6).
5. RZL-012 + sling/pressure garment (until Day 6).

In the first stage of the study, 5 subjects will be randomized into each of the treatment groups. Study outcomes will be assessed up to one week thereafter to determine the need to modify additional study treatments. Subsequently up to 10 additional subjects will be randomized into each of the treatment groups for the second stage of the study.

For each subject, the study will consist of a screening period, baseline period in which subjects will receive a single treatment session of RZL-012 with the assigned treatment and a follow-up period. RZL-012 will be administered during a single treatment session via multiple injections into the submental area under the chin. Subjects will thereafter be monitored for safety and efficacy for at least 84 days.

Each subject will be treated with the same dose of RZL-012 :

- RZL-012 (concentration of injected solution 50 mg/mL RZL-012) of 7.5 mg/0.15 mL/injection point that results in a total dose/volume of 240±30mg mg/4.8±0.6 mL RZL-012,

Each subject will receive additional study treatments in accordance with the treatment group to which the subject is randomized.

4.2 Rationale for Study Design

Because there are 5 different treatment arms, and subjects receive different additional study treatments depending on the treatment arm to which the subject is randomized, blinding of study treatments would be difficult. Therefore, the study will employ an open-label design.

4.3 Rationale for Study Dose

The Phase 2b study (RZL-012-SMF-P2b-US-001) demonstrated that a single treatment session of RZL-012 at a maximal dose of 270 mg into the subcutaneous tissue of the submental area reduces fat and improves appearance of this area. Therefore, Raziel intends to proceed with this dose into Phase 3 clinical trials.

5.0 STUDY POPULATION

5.1 Inclusion Criteria

For a subject to be eligible for this study, he or she must meet **all** of the following inclusion criteria:

1. Is a male or female subject between the ages of 18 and 65 years, inclusive.
2. Has body mass index (BMI) between >22 kg/m² and <40 kg/m².
3. Has SMF bulge that is contiguous and fits to 32 ± 4 injections sites according to a grid with 1 centimeter (cm) distance between injection points.
4. Has grade 3 to 4 of SMF as rated by both the C-CAT and S-CAT.
5. Has stable weight, with no fluctuation of >5 kg in the past 12 months.
6. If female, is not pregnant or breastfeeding based on the following:
 - agree to the use of highly effective contraceptive methods for at least 2 weeks before baseline until 4 weeks after the last day of study drug and a negative serum pregnancy test (β -hCG) at screening and negative urine pregnancy test at baseline; or
 - is abstaining
 - is of nonchildbearing potential defined as clinically infertile as the result of surgical sterilization (hysterectomy, bilateral tubal ligation, and/or bilateral oophorectomy); or
 - is confirmed postmenopausal status (defined as either having amenorrhea for ≥ 12 consecutive months without another cause or documented serum follicle-stimulating hormone (FSH) level > 40 mIU/mL or another documented medical condition (e.g., was born without a uterus))
- NOTE: The following are considered highly effective contraceptive methods: hormonal oral contraceptives, injectables, and patches; intrauterine devices; double-barrier methods (synthetic condom, diaphragm, or cervical cap used with spermicidal foam, cream, or gel); and male partner sterilization.
7. If male (with or without vasectomy), agree to the use of highly effective contraceptive methods as listed above in criteria 7 as well as to use a barrier method, e.g. condom , from study check-in until 7 days after drug injection.
8. Is willing to avoid strenuous exercise for seven (7) days post treatment.
9. Is able to adhere to the visit schedule and protocol requirements and be available to complete the study.
10. Is willing and able to sign an Institutional Review Board (IRB) approved informed consent form (ICF) indicating that they are aware of the investigational nature of the study.

5.2 Exclusion Criteria

Subjects must **NOT** meet any of the following exclusion criteria to be eligible for enrollment:

1. Is unable to tolerate subcutaneous injections
2. Has any systemic disease including but not limited to gastritis or ulcers, renal dysfunction, hypertension, liver disease, glaucoma, diabetes and/or cardiovascular disease, regardless of whether the condition is controlled with medication.
3. Has any contraindications to oral corticosteroids (prednisone), NSAIDs (e.g., Celecoxib) or non-sedative antihistamines (e.g. cetirizine)
4. Has skin laxity (i.e., elastosis, skin crepiness, skin redundancy, skin draping, vertical and/or horizontal skin bands and folds, blunting of cervical mental angle, loss of opposition of skin to underlying neck structures due to skin laxity) that could obscure the evaluation and treatment of SMF.
5. Has any scars, unshaven hair, tattoos, facial hair or jewelry on or near the proposed treatment area.
6. Has presence of structures or confounding factors that may interfere with assessing SMF such as but not limited to enlarged submandibular salivary and/or parotid glands, micrognathia, chin implant, soft tissue volume augmentation of chin and/or jawline, pronounced platysmal bands and deep necklace lines or presence of facial jowls that could obscure the evaluation of SMF.
7. Has a fat bulge under the chin that is too large to be adequately treated by 32 ± 4 contiguous injections on a 1cm grid .
8. Has a fat bulge under the chin that is of an insufficient volume to allow 32 ± 4 injections within a contiguous 1 cm grid.
9. Has significant history or current evidence of a medical, psychological or other disorder that, in the Investigator's opinion, would preclude enrollment in the study.
10. Has an active bacterial, fungal, or viral infection in the proposed treatment area.
11. Has a pre-existing skin condition in the submental region that, at the Investigator's discretion, may confound evaluation or analysis.
12. Has previously had treatments or surgery in the submentum, such as but not limited to, focused ultrasound, radiofrequency, cryolipolysis, liposuction, sodium deoxycholate, or neck lift.
13. Has pre-existing neurological or gastrointestinal condition leading to dysphagia, dysphonia, or facial nerve palsy.
14. Has Dercum's Disease.
15. Has allergic reactions to injectables
16. Has allergic reactions to cetirizine or Celecoxib.
17. Has any pre-existing medical condition other than increased SMF that, at the Investigator's discretion, may result in increased submental fullness, such as but not limited to, thyroid enlargement, goiter, cervical lymphadenopathy, etc.

18. Has a planned fat reduction procedure of any variety to the submental region for the duration of the study.
19. Has medication or a history of coagulopathy.
20. Has a history or family history of venous thrombotic disease.
21. Has been treated chronically at least three (3) months prior to study entry with systemic steroids or immunosuppressive drugs.
22. Has been treated chronically at least one (1) week prior to study entry with non-steroidal anti-inflammatory drugs (NSAIDs)
23. Has used anticoagulation therapies that may increase bleeding or bruising (i.e., aspirin, ibuprofen/Celecoxib, warfarin, vitamins, and herbal preparations) for seven (7) days prior to treatment.
24. Has had treatment with botulinum toxin injections in the neck or chin area within nine (9) months prior to screening.
25. Current participation or participation within three (3) months prior to the start of this study in a drug or other investigational research study.
26. Claustrophobia or MRI incompatible device or implant.

6.0 STUDY INTERVENTION

6.1 Study Intervention Administration

6.1.1 Study Intervention Description

RZL-012 is provided as a sterile liquid solution suitable for injection. It has a concentration of 50 mg/mL. It is packaged in glass vials and supplied in study kits.

Subjects will be treated with additional planned treatments in accordance to their randomization group. In case subjects will be assigned to group 2, they will be injected with 5 mL lidocaine with 1:100,000 epinephrine. In case subjects will be randomized to group 3 or 4 they will receive a prescription to buy in the pharmacy the relevant drugs, i.e. methylprednisolone dose pack (if assigned to group 3) and Celecoxib and cetirizine (in case assigned to group 4). This is in order to allow them to take the drugs at baseline visit (Day 1) prior to RZL-012 injection. Subjects will take medicines 1-2 hours prior to RZL-012 injection and continue after RZL-012 injection per instructions for use for each of the medicines for a total period of 6 days. If subjects are randomized to group 5, they will be given with the pressure garment in the site immediately after injection and will wear the garment up to day 6 after injected. Description of group assignments is described in Table 2.

Table 2– Study Group Treatment

	Group 1	Group 2	Group 3	Group 4	Group 5
Day 1	RZL-012	RZL-012 + 1% lidocaine with 1:100,000 epinephrine (10 minutes prior to RZL-012)	RZL-012 + methylprednisolone dose pack (the first dose of 2 tablets (8mg) is administered 1-2 hours prior to RZL-012) A total of 24 mg (16 mg after RZL-012, as per IFUs)	RZL-012 + 200 mg Celecoxib BID and 10 mg cetirizine BID (the 1 st dose is administered 1-2 hours prior to RZL-012).	RZL-012 + pressure garment
Day 2			20 mg methylprednisolone	200 mg Celecoxib BID and 10 mg cetirizine BID	pressure garment
Day 3			16 mg methylprednisolone	200 mg Celecoxib BID and 10 mg cetirizine BID	pressure garment
Day 4			12 mg methylprednisolone	200 mg Celecoxib BID and 10 mg cetirizine BID	pressure garment
Day 5			8 mg methylprednisolone	200 mg Celecoxib BID and 10 mg cetirizine BID	pressure garment
Day 6			4 mg methylprednisolone	200 mg Celecoxib BID and 10 mg cetirizine BID	pressure garment

BID = twice daily,

[figure not shown]
Subjects will undergo a single treatment session with maximum 36 injections of 7.5 mg RZL-012 each for a total RZL-012 dose of 270 mg. The total injection volume for all groups will be 4.8 mL±0.6.

Subjects will be injected with RZL-012 perpendicularly (90°) to the skin. An ice pack will be placed on the injected area for pain relief immediately after injection. Subjects will remain seated in the injection position for an additional 10 minutes after dosing.

The injection pattern will be based on a submental area shaped grid in which the distance between rows and columns will be 1 cm, as seen in Figure 1 below. The Investigator will choose 32±4 sequential points on the grid that will mark the injected area according to SMF fullness and

convexity. The treatment area boundary: superiorly by a line 1 cm inferior to the mandibular margin, laterally by the sternocleidomastoid muscles, and inferiorly by the hyoid bone.

Figure 1 Submental Injection Pattern

6.2 Preparation/Handling/Storage/Accountability

The RZL-012 solution is supplied ready to use. The RZL-012 kits, each comprised of 2 vials, should be stored in the site pharmacy or clinic at monitored room temperature conditions (22 ± 7 °C) and protected from light. They should be kept in a secure location physically separated from standard clinic or office drug supplies.

RZL-012 is administered to the subject on the study site by the study investigator. The vials should be manually shaken prior to injection.

The following procedures prior to injection into the SMF will be applied:

1. The lower face and anterior neck will be cleaned with an appropriate topical antiseptic.
2. Ice/cold pack or topical local anesthesia (i.e., lidocaine cream) may be used prior to drug administration to enhance subject's comfort.
3. The treatment area will be bounded superiorly by a line 1 cm inferior to the mandibular margin, laterally by the sternocleidomastoid muscles, and inferiorly by the hyoid bone.
4. Injection grid pattern will be applied by pressing the grid firmly onto the clean, dry skin, with the printed grid pattern facing the skin. The grid paper backing will be thoroughly wetted with a cotton pad soaked with sterile water. After 15 seconds, the grid cover will be peeled off.
5. An area of 32 ± 4 adjacent injection points will be determined following the Investigator's evaluation.
6. Syringes will be filled with 1 mL RZL-012 and the number of syringes will be compatible with the total volume of injection. Up to six (6) syringes for a total volume of 5.4 mL will be used.

7. All injections will be administered perpendicularly in 90 degrees, using a 1 mL Luer-lock syringe and a 29G or 27G x 1/2" needle, respectively.
8. The hole of the needle should be pointing into the middle of fat layer and the injection direction should be towards the earth. An attempt to pull the plunger should be made prior to injecting to ensure no blood is coming out. If so, the plunger should be pushed down to inject 0.15 ml the medicine. The formulation is viscous; therefore, resistance is expected during injection.
9. Immediately following completion of the injections, an ice/cold pack will be applied for immediate pain relief. It will be held by the subject for at least two (2) minutes.
10. The Investigator will record the number of injections administered for each subject.

The injection pattern used will be based on an existing grid in the shape of the submental area, where distance between injection rows will be 1 cm and distance between the injection columns will be 1 cm.

The number of injections for each subject will be determined by the Investigator according to fullness of SMF but will not be lower than 28 injections or higher than 36 injections. Total injection volume and number of injection per subject should be recorded on medical records.

All study drug received by the Investigator will be inventoried and accounted for in a Dispensing Log.

A maximal of 2 vials will be used for each subject. All open vials will be kept until the end of study when the Sponsor will determine if study drug should be returned or destroyed.

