	
Subjects will be injected with RZL-012 perpendicularly (90°) to the skin. An ice pack will be placed on the injected area for pain relief immediately after injection. Subjects will remain seated in the injection position for an additional 10 minutes after dosing.
 
The injection pattern will be based on a submental area shaped grid in which the distance between rows and columns will be 1 cm, as seen in the figure below. The Investigator will choose 32±4 sequential points on the grid that will mark the injected area according to SMF fullness and convexity. The treatment area boundary: superiorly by a line 1 cm inferior to the mandibular margin, laterally by the sternocleidomastoid muscles, and inferiorly by the hyoid bone.
 

Safety Analysis
	
AEs will be collected and reviewed to evaluate the safety and tolerability of RZL-012. AE collection will begin after dosing and will end at on Day 84. For subjects having unresolved AEs on Day 84, an unscheduled visit will be set 6-8 weeks after Day 84 to verify the resolution of the AE.
 
Other safety measures will include vital sign measurements, laboratory parameters, ECG, and treatment area evaluation including, but not limited to evaluation of edema, bruising, dysphasia, dysphonia, erythema, dyspigmentation, induration, numbness, pain, paresthesia, , pruritus, skin ulceration and necrosis, injury to the marginal mandibular nerve, vascular and nerve injury and tissue damage to nearby vulnerable anatomic structures. Specifically, swelling severity will be assessed in each visit, subjects will be asked about their pain levels. Pain at injection site will not be recorded as an AE but the information regarding pain will be obtained from the VAS scores completed by the subject. AEs related to nerve injury will be AEs of special interest. Concomitant medications will be recorded.

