6.4 Prior and Concomitant Medications

Concomitant medications are defined as medications taken any time after the start of dosing until discharge assessments. All concomitant medication, including blood and blood products, dietary supplements, and non-prescription drugs, will be listed at screening/baseline. Each entry will include the treatment's start date, treatment name (generic), reason for use, dosing regimen (dose and frequency of use), route of administration, and stop date (if applicable). Study subjects will be routinely questioned for changes in the administration of concomitant medication during the trial and changes should be updated from medical records as well.

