8.14 Visual Analog Scale (VAS)

Pain will be assessed as part of the AEs using Visual Analog Scale (VAS). A scale between 0 to 10 will describe the pain level, where 0 represents no pain and 10 score is intolerable pain. A score of 1-3 is categorized as mild, 4-6 is moderate and 7-10 is severe. VAS will be assessed on Day 1 (after injection), Day 2, Day 4, Day 7, Day 14, Day 21, Day 28, Day 56 and Day 84.

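### Section 6.2 permits lidocaine cream or ice before RZL-012 in any group with no rule for use, which could blur the Day 1 pain comparison of the injected-lidocaine group with the others

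*Combined protocol and SAP*

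**What the plan says.** Section 6.2 lists the steps before injection once, for all subjects. Step 2 reads: "Ice/cold pack or topical local anesthesia (i.e., lidocaine cream) may be used prior to drug administration". The stated purpose is the subject's comfort. No group is excluded, no criterion is given, and the text does not say who decides.

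The primary objective (Section 3.1.1) is to "compare the benefits of lidocaine, methylprednisolone, Celecoxib + cetirizine or compression garments on RZL-012-induced adverse events". The Study Rationale puts the aim as follows: "This clinical trial will assess ways to reduce AEs related to swelling and pain".

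Group 2 receives 5 mL of 1% lidocaine with epinephrine by injection, 10 minutes before RZL-012 (Section 4.1). Group 1 receives no study add-on.

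Pain is measured by VAS only. The Synopsis says: "Pain at injection site will not be recorded as an AE but the information regarding pain will be obtained from the VAS scores". Section 9.4 repeats that injection-site pain is not recorded as an AE. On timing, Section 8.14 says: "VAS will be assessed on Day 1 (after injection), Day 2, Day 4, Day 7", and then continues to Day 84.

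Ice after the injection is handled differently, because Section 6.1.1 sets it for everyone: "An ice pack will be placed on the injected area for pain relief immediately after injection".

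**The concern.** Group 2 is a test of a local anesthetic. Step 2 makes a second route of the same drug, and a second comfort measure, optional in every group. Randomization balances the groups at assignment. It does not protect against a co-treatment chosen afterwards by people who know the assignment.

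Subjects about to have 28 to 36 injections without injected anesthetic might be offered, or might ask for, cream or ice more often than Group 2 subjects. The Group 2 contrast on early pain would then shrink. If use were more common in Group 2, the contrast would grow.

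The reading most exposed is the Day 1 post-injection VAS, which lies closest to the single lidocaine dose. At stake is how far a difference, or lack of one, on that reading can be credited to injected lidocaine. Stage 1 outcomes in 5 subjects per group also inform whether the add-on treatments are modified (Section 4.1).

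**Working it through.** **1. The plan's own figure.** The stated sample size is 75. Two stages in five groups give 5 × 5 + 5 × 10 = 75, which equals 5 × 15. It reproduces, and this point does not dispute it. The plan gives no power, effect size or SD for pain.

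**2. Can use depend on the arm?**
- Section 4.2: the trial is open-label.
- Synopsis (Screening Period) and Section 1.2: randomization takes place at screening, before Day 1.
- Section 6.2: the study investigator gives RZL-012, and step 2 is permissive and not split by group.

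Together these allow arm-dependent use. Nothing in the Synopsis, in the group table of Section 6.1.1 or in Section 6.4 restricts it.

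**3. Would use be visible in the data?**
- Section 6.2 asks for the injection count, "The Investigator will record the number of injections administered for each subject", and for the total volume. It does not ask for cream or ice.
- Cream: Section 6.4 says "Concomitant medications are defined as medications taken any time after the start of dosing until discharge assessments", which taken literally leaves out cream applied beforehand. The same section also lists medication, including non-prescription drugs, at screening/baseline, and Section 1.2 schedules concomitant medication on Day 1. Capture is therefore probable but not certain.
- Ice is not a medication, and no section requires pre-injection ice to be recorded.

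**4. How much of the pain data is exposed?** Section 8.14 schedules VAS on Days 1, 2, 4, 7, 14, 21, 28, 56 and 84, nine readings in all. Day 1 is one of nine. It is one of four (Days 1, 2, 4 and 7) if the Stage 1 review covers the first seven days, which is an assumption.

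**5. Scale, under assumed inputs.** Let e be the fall in a user's Day 1 VAS on the 0–10 scale, k the number of extra users in one arm, and n the arm size. The shift in that arm's mean is e × k / n. The documents give neither e nor k. Take e = 1 to 3 points.

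| n | k | Calculation | Shift (points) |
|---|---|---|---|
| 5 (Stage 1) | 1 | 1 × 1/5 to 3 × 1/5 | 0.2 to 0.6 |
| 5 (Stage 1) | 3 | 1 × 3/5 to 3 × 3/5 | 0.6 to 1.8 |
| 15 (full arm) | 1 | 1 × 1/15 to 3 × 1/15 | 0.07 to 0.2 |

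**6. The same effect as a proportion.** Suppose a share c of the comparator group uses cream or ice, this gives a share r of the benefit of injected lidocaine, and Group 2 has no such use. The observed contrast is then the true contrast × (1 − c × r).
- c = 0.25, r = 0.25: loss of 0.0625, about 6%.
- c = 0.5, r = 0.5: loss of 25%.
- c = 1, r = 0.5: loss of 50%.

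Both c and r are assumed. If the extra use were in Group 2 instead, the contrast would be enlarged.

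**The case against.** The case for leaving step 2 alone has several parts.

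- *Comfort measures are reasonable for people having 28 to 36 injections.* This stands, and the fix should keep one.
- *Nothing shows that a measure applied to the skin changes a VAS taken after the injection.* RZL-012 is aimed at the middle of the fat layer, everyone receives ice afterwards, and Section 8.14 times the first reading only as after injection. This stands. The effect could be small or nil.
- *The primary endpoint is the whole safety profile, summarized descriptively by arm (Sections 3.2.1 and 9.3).* This limits the consequence, since no formal test is affected. It does not remove the problem: the objective is comparative, and a descriptive contrast can be biased too.
- *Subjects already know their arm when they score pain.* True, and accepted in Section 4.2. Unequal co-treatment is a separate source of difference, and this one can be removed.

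A reader might go further in four ways that the documents do not support:

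- That step 2 contradicts the definition of Group 1. Section 4.1 describes groups with or without additional study treatments, so the name of Group 1 means no study add-on. It does not mean no comfort measure, since Group 1 also gets ice after the injection.
- That the protocol gives the choice to the investigator. This is an inference from the permissive wording; a subject's request could equally prompt use.
- That cream would go unrecorded. It is probably captured.
- That the Stage 1 decision turns on Day 1 pain. Section 4.1 refers only to study outcomes in general.

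**Conclusion.** The point holds as a minor one. As written, step 2 permits pre-injection cream or ice to differ by arm in a trial where the arm is known and one arm is injected lidocaine. The comparison of Group 2 with the other groups on Day 1 VAS could be blurred in either direction.

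The size is unknown. The range of 0.2 to 1.8 points for a five-subject arm comes wholly from an assumed effect of 1 to 3 points and an assumed excess of 1 to 3 users; its upper end combines the two largest assumptions and is not an estimate. The reach is mainly one of nine VAS readings. No effect on swelling is claimed, and there is no evidence that use will in fact differ. The one clear recording gap is pre-injection ice.

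**What to change.** 1. Reword step 2 of Section 6.2 so that the pre-injection comfort measure is the same in all five groups. For example: no topical anesthetic, and an ice/cold pack for every subject before RZL-012. This matches the uniform ice after injection.
2. Add one Day 1 CRF field recording any cream or ice used before dosing, so that departures are visible and Day 1 VAS can be described by use. Such a description would not be a randomized comparison, since use follows assignment.

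Cream for everyone would also be uniform, but Group 2 would then test injected lidocaine on top of cream. That is a different question, so the ice-only rule is the simpler choice.

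The cost is one reworded step and one CRF field, with no change to the sample size or the visits. The downside is that subjects and investigators lose the option of cream.
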